3.5.12 Day 35 (± 2 Days); Follow-up Telephone Contact

Applicable to patients NOT receiving prolonged treatment

On Day 35, the Clinical Trial Unit will contact patients not receiving prolonged treatment and ask questions from the patient questionnaire relating to VVC symptoms (itching, burning, or irritation). Patients will also be asked questions on concomitant medications, recurrence, and

Protocol Version 3.0, 24Oct2018

LINK Medical Research | Protocol template

Version 2.0 | Effective date 17Apr2018

AEs, if any. In addition, patients will self-collect vaginal samples by swab for sequencing and send samples by post to laboratory.

Procedures performed:

- Vulvovaginal candidiasis recurrence
- Symptoms (itching, burning, or irritation) of VVC evaluated by patients according to the scoring scale
- Vaginal swab for sequencing
- Recording of:
 - concomitant medications, and
 - adverse events

3.5.13 Day 42 (± 2 Days); Follow-up Telephone Contact

Applicable to patients receiving prolonged treatment

Patients receiving prolonged treatment will be contacted over telephone by the Clinical Trial Unit on Day 42 and asked questions from the patient questionnaire relating to VVC symptoms (itching, burning, or irritation). Patients will also be asked questions on recurrence, concomitant medications, and AEs, if any. Patients will collect vaginal samples by self-swab to be sent by post to laboratory for sequencing.

Procedures performed:

- Vulvovaginal candidiasis recurrence
- Symptoms (itching, burning, or irritation) of VVC evaluated by patients according to the scoring scale
- Vaginal swab for sequencing
- Recording of:
 - concomitant medications, and
 - adverse events

3.6 Early Withdrawal Procedures

See [Section 4.6](#) for withdrawal procedures. Patients refusing to visit the site for follow-up visits shall be contacted by telephone, if possible, to collect answers to the patient questionnaire, and AEs, if any. Patients receiving fluconazole on Day 14 will be followed up for safety assessments.

4 SELECTION OF STUDY POPULATION

4.1 Patient Population and Number of Patients

This study will include patients with VVC. Twenty-four (24) patients are planned to be treated under this CIP.

Post-menarchal, pre-menopausal females aged 18 years or older seeking treatment for symptoms of VVC at study sites' gynecological clinics may be informed about the study and asked about their willingness to participate.

Patients may also contact the site directly and book appointments after seeing study advertisement on social media.

The Investigator must always use IEC-approved patient information that must not be changed without prior Sponsor and IEC approvals, see [Section 11](#) for further details.

Patients who have signed the ICF shall be listed on a screening-and-inclusion log together with an assigned screening number. Patients not fulfilling *all* inclusion criteria as described in [Section 4.2](#), or fulfilling *any* of the exclusion criteria listed in [Section 4.3](#), shall be considered screening failures. Screening failure reasons shall be stated in both the Screening Visit electronic case report form (eCRF) pages and the screening-and-inclusion log.

4.2 Inclusion Criteria

Inclusion and exclusion criteria in the fungal study should follow the FDA Vulvovaginal signs-and-symptoms score:

- Adult, post-menarchal, pre-menopausal women aged 18 years or older
- Diagnosis of VVC, defined as having a white or creamy vaginal discharge plus the following findings:
 - *At least* 2 of the following signs and symptoms of VVC that are characterized as *at least* moderate: itching, burning, irritation, edema, redness, or excoriation.
 - Potassium hydroxide (KOH) or saline preparation from the inflamed vaginal mucosa or secretions revealing yeast forms (hyphae or pseudohyphae) or budding yeasts.
- Having decisional capacity and providing written informed consent.
- Negative urine pregnancy test at screening.
- Refrain from using any intravaginal products (i.e., contraceptive creams, gels, foams, sponges, lubricants, or tampons, etc.) during the study period.
- Refrain from sexual intercourse or use a condom until Day 7
- Signed informed consent and willing and able to comply with all study requirements.

4.3 Exclusion Criteria

- Patients with known or apparent signs of other infectious causes of VVC (BV, *Trichomonas vaginalis*, *Neisseria gonorrhoeae*, *Chlamydia trachomatis*, Herpes simplex, or human papillomavirus) at screening.
- Patients who are pregnant or breastfeeding.
- Patients who were treated for VVC within the past 14 days.
- Patients who are currently receiving antifungal therapy unrelated to VVC or has taken antifungal therapy within the past 14 days.
- Patients who have used pH-modifying vaginal products within the last 14 days.
- Patients who have received an investigational drug in a clinical investigation within 30 days prior to screening.
- Known/previous allergy or hypersensitivity to any product constituent or fluconazole.

- Any medical condition that in the Investigator's judgments would make the patient unsuitable for inclusion.

4.4 Withdrawal and Termination Criteria

Subjects shall be informed through the ICF about their rights to withdraw from the study at any time, without prejudice to further treatment or medical care. The Investigator may, at his or her discretion, withdraw a patient from the study and discontinue study treatment and assessments at any time. The specific reasons for discontinuing a patient from the study shall be documented in the eCRF.

4.5 Reasons for Withdrawal

Reasons for patient withdrawal include, but are not limited to:

Informed consent withdrawal:	The patient may withdraw from the study or be withdrawn by a legal representative, if applicable, at any time without stating a reason and without prejudice to further treatment or medical care.
Safety reasons:	The Investigator or Sponsor may withdraw patients if judged that an AE poses an unacceptable risk or consequence to the patient.
Medical reasons:	The Investigator may withdraw patients if judged that a medical condition poses an unacceptable risk or consequence for the patient to continue in the study. The rationale and the medical condition responsible for the Investigator-initiated withdrawal shall be documented.
Lost to follow-up:	Reasonable efforts shall be made to reach patients not returning for scheduled visits or not being reachable by telephone. Such efforts may include, e.g., calling the patient at least 3 times at different hours and leaving voice messages.
Other reasons:	Includes but are not limited to failure of the patient to comply with study procedures or requirements

4.6 Handling of Withdrawals

If a patient withdraws from the study before study completion, the reason for withdrawal should be sought and recorded on the eCRF. If the withdrawal is due to the performance or safety of the investigational device, the Investigator will ask for permission to follow-up patients outside of the study. If a withdrawal occurs during a study visit, the eCRF for that specific visit shall be completed as far as possible.

Any AEs should be followed up until the AE is resolved or the Investigator decides that the AE is stable and needs no further follow-up. The last day for follow-up will be the study Day 35 if not receiving prolonged treatment or Day 42 if receiving prolonged treatment. AEs ongoing at study Day(s) 35 or 42 shall be assessed as chronic or stable. Wherever possible, end-of-study assessments should be carried out at the time of withdrawal.

4.7 Replacements

Withdrawn or discontinued patients shall not be replaced or re-entered into the study

4.8 Sponsor Termination of Study

Although the Sponsor has every intention of completing the study, the Sponsor reserves the right to discontinue the study at any time for clinical or administrative reasons. In such a case, Investigators will be informed of additional procedures to be followed to ensure that adequate consideration is given to the protection of patient's interest.

If the study is prematurely terminated or suspended for any reason, the Investigator has to inform the patients and to assure appropriate patient follow-up. The Sponsor should promptly inform the study sites, and the RA on the termination or suspension and the reason(s) for the termination or suspension. The IEC should also be informed promptly and provided with the reason(s) for the termination or suspension by the Sponsor or by the Investigator, as specified by the applicable regulatory requirements.

5 TREATMENTS

5.1 Investigational Product

The investigational product, Gedea Pessary (commercial name *p*Hyph), is a GDL-and-NaG containing pessary to be administered vaginally with a CE-marked vaginal tablet applicator (Schägner GmbH, Steinmauern, Germany). The device is intended to treat vaginal Candida infections, see [Figure 2](#) and [Figure 3](#) for product image and applicator label. Gedea Pessary is a Class IIa medical device according to MDD 93/42/EEC (the Swedish regulation SFS 1993:584 and LVFS 2003:11).

NOTE: The terms investigational product, Gedea Pessary, investigational device, pessary, and vaginal pessary are used interchangeably in the CIP

Gedea Pessary is a white, convex, bullet-shaped tablet, approximately 2 cm in length, contract-manufactured by Galenica AB (Malmö, Sweden). The pessary is slow-release formulated, administering 300 mg GDL and 367.5 mg NaG over 45 hours. Each patient will administer a total of 4 pessaries in the study or 8 if receiving prolonged treatment. The investigational products will be packed in blister packs containing 4 pessaries labeled with *Gedea Pessary* and batch number. Blisters will be packed together with 4 vaginal tablet applicators in a cardboard-box labeled with *Gedea Pessary, for investigational use only*, production date, and expiry date ([Figure 4](#)).

It is the responsibility of the Investigator to ensure that the investigational products are stored in their original packaging in a secure location with access only by authorized personnel, separate from other medications. The investigational product shall be stored at room temperature (15°C -25°C), protected from direct sunlight or freezing. The investigational products *must not* be used outside of the study. For further reference, refer to the IB.

Instructions for use will be distributed at the first visit, advising patients on how to use the product together with the applicator. Briefly, patients will be instructed to: wash their hands and vaginal area prior to use; place a tablet into the applicator and insert as far into the vagina

as is comfortable (without forcing), or until half of the applicator is inside; discard the applicator after use; not use tampons or other vaginal products while using this product.

[figure not shown]
Figure 2 Gedea Pessary and Applicator

Figure 3 Vaginal Tablet Applicator Label

Figure 4 Investigational Product Label

5.1.1 Investigational Product Accountability

The investigational products may be released to the Investigator when the clinical trial agreement (CTA) has been signed by all involved parties and appropriate approvals has been given from the IEC.

The Investigator is responsible for full traceability of the investigational product from the manufacturer to patients until return or disposal. This shall be ensured by use of product accountability records, documenting:

- Product quantity at storage, and
- Deliveries to-and-from storage.

Shipping records of investigational product deliveries from the manufacturer shall be kept at study sites, including *at least* the following information:

- Investigational product name and quantity received,
- Delivery date,
- Batch number, and
- Expiry date.

Dispensing logs shall be kept at study sites, documenting *at least* the following information:

- Investigational product name,
- Batch number,
- Expiry date,
- Dispense date,
- Number of units used,
- Patient receiving the investigational product, and
- Number of units remaining in stock.

Any nonfunctioning devices or applicator shall be documented. All unused or expired investigational products must be returned to the Sponsor for destruction unless otherwise stated in writing by the Sponsor. Any used, or opened unused materials *must not* be reused.

5.2 Additional Products and Material

The Sponsor will provide kits for vaginal swabs for culturing and sequencing. The Sponsor will provide the study sites with pH meters for vaginal pH analysis. Study sites will provide urine pregnancy tests (urinary human chorionic gonadotropin [U-HCG]) and other materials, as applicable.

The Investigator is responsible for full traceability of the vaginal swabs from the manufacturer to patients until return or disposal. This shall be ensured by use of accountability records documenting quantity at storage and deliveries to and from storage.

Shipping records of vaginal swab-kit deliveries from the manufacturer shall be kept at study sites, including *at least* the following information:

- Swab kit batch number and quantity received,
- Delivery date, and
- Expiry date.

Dispensing logs shall be kept at study sites, documenting *at least* the following information:

- Swab kit batch number,
- Expiry date,
- Dispense date,
- Number of units used,
- Patient receiving the swab kit, and
- Number of units remaining in stock.

All unused or expired swab kits must be returned to the Sponsor for destruction unless otherwise stated in writing by the Sponsor. Any used, or opened unused materials *must not* be reused.

5.2.1 Rescue Medication

Fluconazole will be used as rescue medication in this investigation, and patients will receive a prescription for fluconazole if considered necessary to relieve their VVC symptoms on Day 14. Patients withdrawing at any point in the investigation may receive fluconazole if considered necessary by the Investigator. The dose of fluconazole will be decided by the Investigator on an individual basis. The use of rescue medication will be recorded in the eCRF.

5.3 Selection of Investigational Device and Doses

Refer to [Section 3.2](#)

5.4 Treatments Administered

The pessary will be self-administered vaginally by the patient. The pessary should be inserted high into the vagina. The pessary should be used with the co-supplied vaginal tablet applicator. The patients should insert the applicator gently and deeply into the vagina, and then slowly depress the plunger to release the pessary. Instructions for use will be distributed to patients at the first site visit. See also [Section 5.1](#).

5.5 Method of Assigning Patients to Treatment Groups

Not applicable

5.6 Blinding

Not applicable

5.7 Prior and Concomitant Medication

Information about any concomitant medication, including OTC medications and vitamins taken by patients during the study and within 14 days prior to inclusion shall be documented in the eCRF. The generic name or trade name, dosage, and reason for use shall be recorded for all medications.

NOTE: Antifungal medication during the study and within 14 days prior to inclusion is strictly prohibited

See [Appendix 1, Section 3](#) for specific questions.

5.8 Treatment Compliance

Patients will be asked about investigational product administration by telephone on Day 4 and at the site on Day 7, and also on Day(s) 11 (telephone) and 14 (site) if receiving prolonged treatment. No other measurements of treatment compliance will be made.

6 CLINICAL PERFORMANCE

6.1 Clinical Performance Assessments

Assessments described below in [Section 6.1.1](#), gynecological examination, will be used to collect the following 6 vulvovaginal signs and symptoms:

- Vulvovaginal signs of: erythema, edema, and excoriation; and
- Vulvovaginal symptoms of itching, burning, and irritation.

The intensity of each of the signs and symptoms will be scored as:

- 0 = none (absent),
- 1 = mild (slight),
- 2 = moderate (definitely present), or
- 3 = severe (marked, intense).

The scores will be added together and the sum defined as the CVVS score.

A CVVS score equal to or below 3 on Day 7 will be defined as clinical cure, and is a co-primary study endpoint together with safety and tolerability evaluation.

The CVVS score will also be used for the following secondary endpoints:

- Proportion of patients having a reduction in CVVS score on Day 7 compared to Day 0.
- Change in the CVVS score from Day 0 to Day 7.
- Recurrence rate at Day 14 and Day 35, defined as the proportion of patients clinically cured at Day 7 and thereafter responding “yes” to a yes/no question from the patient questionnaire on whether the symptoms have recurred.
- Proportion of patients receiving prolonged treatment.
- Clinical cure rate on Day 14, defined as the absence of signs and symptoms of VVC in terms of having a CVVS score equal to or below 3.
- Proportion of patients having a reduction in CVVS score on Day 14 compared to Day 0.
- Change in the CVVS score from Day 0 to Day 14.
- Recurrence rate at Day 21, and Day 42, defined as the proportion of patients clinically cured at Day 14 and thereafter responding “yes” to a yes/no question from the patient questionnaire on whether the symptoms have recurred.
- Proportion of patients receiving prescription for fluconazole at Day 14.

Assessments described in [Section 6.1.2](#), patient questionnaire, will be used to assess the following secondary endpoints:

- Proportion of patients having a reduction in the sum of the 3 vulvovaginal symptoms scores (itching, burning, and irritation) on Day 4 and Day 7, compared to Day 0.
- Change in the sum of the 3 vulvovaginal symptoms scores (itching, burning, and irritation) from Day 0 to Day 4 and Day 7.
- Usability, measured by patient questionnaire.

- Proportion of patients having a reduction in the sum of the 3 vulvovaginal symptoms scores (itching, burning, and irritation) on Day 11, Day 14, Day 21, and Day 42, compared to Day 0.
- Change in the sum of the 3 vulvovaginal symptoms scores (itching, burning, and irritation) from Day 0 to Day 11, Day 14, Day 21, and Day 42.

6.1.1 Gynecological Examination

Patients will have gynecological examinations by the Investigator or authorized designee on Day(s) 0 and 7; or Day(s) 0, 7, and 14 if receiving prolonged treatment, in order to assess vulvovaginal signs of erythema, edema, and excoriation. During the examinations, patients will also be asked about any vulvovaginal symptoms of itching, burning, and irritation.

NOTE: The Investigator will always assess *vulvovaginal signs* of erythema, edema, and excoriation. Vulvovaginal *symptoms* of itching, burning, and irritation will always be assessed by patients themselves and asked about by the Investigator at site visits.

6.1.2 Patient Questionnaire

The questionnaire can be found in [Appendix 1](#).

The Clinical Trial Unit will call the patients on Day(s) 4, 14 and 35; or Day(s) 4, 11, 21, and 42 if receiving prolonged treatment; and ask questions from the patient questionnaire relating to vulvovaginal symptoms (itching, burning, or irritation), usability, concomitant medications, and AEs, if any.

Questions from *Section 1* in the patient questionnaire relating to vulvovaginal symptoms of itching, burning, and irritation will be asked to patients over telephone on Day(s) 4, 14, and 35; or Day(s) 4, 11, 21, and 42 if receiving prolonged treatment. A recurrence question will be asked to patients at Days(s) 14 and 35 if not receiving prolonged treatment and at Days(s) 21 and 42 if receiving prolonged treatment.

Questions from *Section 2* in the patient questionnaire relating to usability in will be asked to patients on Day 7, and Day 14 if receiving prolonged treatment.

Questions from *Section 3* and *Section 4* in the patient questionnaire relating to concomitant medications and AEs, respectively, will be asked to patients at each visit/telephone contact.

7 SAFETY AND TOLERABILITY ASSESSMENTS

7.1 Medical and Surgical History

Medical and surgical history will be collected during the Screening Visit.

7.2 Clinical Laboratory Evaluation

Vaginal samples will be collected by vaginal swab on Day(s) 0 and 7 by the Investigator and on Day 35 by patients (also on Day 14 by Investigator and Day 42 by patients if receiving prolonged treatment). Collected samples will be used accordingly:

- The potassium hydroxide (KOH) test for fungus from samples from Day(s) 0, 7, and 14 if receiving prolonged treatment. Briefly, vaginal samples are covered with

10% – 20% KOH and inspected by microscope. Presence of hyphae indicate Candida and will serve as an immediate, preliminary VVC diagnosis.

- Samples collected on Day 0 will be sent to laboratory and cultured to confirm the VVC diagnosis. Time for lab results is approximately 1 week; patients will be included based on the KOH test as described above.
- Sequencing of samples collected on Day(s) 0, 7, and 35 (by patients). If receiving prolonged treatment, samples will be collected on Day(s) 0, 7, 14, and 42 (by patients). These samples will be analyzed after study completion to assess effects of the investigational product on the vaginal microbiome.

Patients' vaginal pH will be measured for assessments of investigational product *in vivo* duration on Day(s) 0 and 7. Vaginal pH lower at follow-up visits compared to Day 0 indicate appropriate release duration.

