3.2 Rationale for Study Design

As described in [Section 1.1](#), VVC is a major clinical concern, and new effective interventions not associated with antibiotic resistance and major drug interactions would be valuable additions to the current treatment arsenal. This study aims to investigate the clinical performance and safety of the Gedea Pessary containing GDL and NaG in treating VVC.

Previous *in vitro* data show that GDL inhibits both bacterial and fungal biofilm formation, and transforms *Candida* to a non-adhesive form (see [Section 1.2](#)). In addition, a device comparable to Gedea Pessary with regards to its pH-lowering and biofilm-inhibiting properties, used for treating BV, have shown high cure rates.⁴⁴ Data also indicate that GDL is tolerable and does not pose any special risk to humans ([Section 1.3.1](#)).

Based on this, it may be argued that a trial involving patients is justified due to the widespread clinical problem of VVC and the issues involving current therapies (see [Section 1.1](#)). Further, due to that the pessary has not been evaluated clinically prior to this study and the lack of proper comparators, a single-arm design has been chosen, allowing evaluation of clinical performance on a smaller number of patients. Due to the open-label design, risks for introducing assessor bias have been minimized by the use of well-defined and documented scales, as well as objective laboratory assessments.

The dose of 300 mg GDL and 376.5 mg NaG administered 2 days apart on Day(s) 0, 2, 4, and 6^a was chosen based on pre-clinical data, specifically an *in vitro* dissolution test of the Gedea Pessary using a vaginal fluidic model (see IB). Measurements of pH in the *in vitro* dissolution test showed a pH-decrease duration of approximately 45 hours.

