3.5.4 Day 6; Treatment Administration

Procedures performed:

- Treatment self-administration by patients

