3.5.5 Day 7 (+2 Days); Follow-up Visit

Patients will visit the clinic on Day 7 to have gynecological examination performed. The Investigator or an authorized designee will assess the presence of vulvovaginal signs (erythema, edema, or excoriation) and symptoms (itching, burning, or irritation) and score each sign and symptom.

Vaginal samples will be examined by microscope to reveal yeast forms (hyphae or pseudohyphae) or budding yeast and secretion samples collected by swab to be used for sequencing analysis of the vaginal microbiome. Vaginal pH will also be assessed.

If VVC symptoms are still present, patients will have prolonged treatment and receive additional doses of investigational product to be administered at home on Day(s) 7, 9, 11, and 13.

In addition, patients will be asked questions from the patient questionnaire to assess: usability; concomitant medications; and AEs, if any.

Procedures performed:

- Gynecological examination by Investigator or authorized designee evaluating signs (erythema, edema, or excoriation) and symptoms (itching, burning, or irritation of VVC according to the scoring scale
- Fungal KOH microscope assessment
- Vaginal swab for sequencing
- Vaginal pH
- Recording of:
 - concomitant medications,
 - adverse events, and
 - usability
- Treatment dispensing and self-administration by patients if receiving prolonged treatment

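### One vaginal pH reading, nominally 24 to 72 hours after the last pessary, cannot support the stated inference of appropriate release duration

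*Protocol*

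**What the plan says.** Protocol section 7.2 gives the purpose of the measurement: "Patients' vaginal pH will be measured for assessments of investigational product" in vivo duration, on Days 0 and 7. It then sets the interpretation: "Vaginal pH lower at follow-up visits compared to Day 0 indicate appropriate release duration". SAP section 7.10.1 repeats that sentence under extent of exposure and promises summary statistics.

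The rule names no number of hours. The expected duration appears elsewhere. Protocol section 3.2 reports that the in vitro "dissolution test showed a pH-decrease duration of approximately 45 hours" and uses this test to justify the dose and its two-day spacing. Protocol section 5.1 describes the pessary as "administering 300 mg GDL and 367.5 mg NaG over 45 hours", and SAP section 2 says the same.

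On timing, the last first-course pessary falls under "3.5.4 Day 6; Treatment Administration", which has no window. The next contact is "3.5.5 Day 7 (+2 Days); Follow-up Visit", where "Vaginal pH will also be assessed". Doses for prolonged treatment are dispensed at that visit.

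On analysis, SAP section 7.9.3 treats Day 7 pH as an exploratory continuous variable to be described only, and SAP section 8.4 derives one change from Day 0 to Day 7.

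**The concern.** The rule turns a single comparison (pH now against pH at Day 0) into a statement about how long the product releases. A duration can be read from one time point only if that point lies usefully in relation to the duration in question. Here the on-schedule reading comes well before 45 hours and the late ones come around or after it. A lower pH on schedule is what one would see from a product lasting 45 hours, and also from one that stops soon after the reading. An unchanged pH at the end of the window is what one would see from a product that performed exactly as described.

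This is the only in vivo check on duration that the protocol plans, and the spacing of doses is justified by the in vitro figure. The interpretation is already written into both documents, so it could pass into the clinical investigation report, on which Protocol section 11.4 says all publications must be based.

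**Working it through.** **Inputs**

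- Last pessary before the reading: Day 6, no window (Protocol 3.5.4). No dose is scheduled between this and the reading, because prolonged-treatment doses are handed out at the visit (Protocol 3.5.5).
- Reading: Day 7, 8 or 9 (Protocol 3.5.5). The Day 14 visit lists no pH (Protocol 3.5.10).
- Reference duration: about 45 hours (Protocol 3.2 and 5.1; SAP 2). It is an in vitro result taken from the Investigator's brochure, and the documents give no data from which to reproduce it.
- Clock times of insertion and reading: not specified. Protocol 5.8 provides only for asking patients about administration.

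**Formulas**

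Nominal hours since last pessary = (visit day − 6) × 24. With unknown clock times, the calendar-day limits are the nominal value ± 24 hours.

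| Visit day | Nominal hours | Nominal minus 45 h | Calendar-day limits |
|---|---|---|---|
| 7 | (7 − 6) × 24 = 24 | −21 | 0–48 |
| 8 | (8 − 6) × 24 = 48 | +3 | 24–72 |
| 9 | (9 − 6) × 24 = 72 | +27 | 48–96 |

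**Sensitivity to clock time** (assumed: visits between 08:00 and 17:00)

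| Visit day | Dose at 22:00 | Dose at 07:00 |
|---|---|---|
| 7 | 10–19 h | 25–34 h |
| 8 | 34–43 h | 49–58 h |
| 9 | 58–67 h | 73–82 h |

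Under these assumptions Day 7 readings lie before 45 hours and Day 9 readings after it. Day 8 readings can fall on either side.

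**What each result can mean**

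- Lower pH, nominal Day 7: compatible with any duration of about 24 hours or more, so it cannot tell 24 from 45.
- pH not lower, nominal Day 7: would count against a 45-hour effect.
- Lower pH, nominal Day 9: suggests an effect beyond 45 hours, or another cause.
- pH not lower, nominal Day 9: compatible with 45 hours, and also with a much shorter duration.

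**Whether the analysis separates these cases**

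It does not. CRF visits serve as analysis visits (SAP 7.1.4), so Days 7, 8 and 9 enter one summary. Relative day counts from the first administration (SAP 7.1.3), not the last. There is no control arm, and four doses precede the reading, so a drop need not reflect the last pessary, or the product at all.

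**The case against.** The strongest reply is that little depends on this. Vaginal pH is exploratory, no threshold or test is attached to it, and the planned output is descriptive. That stands, and it limits the weight of the point. A reader might infer that the trial will go on to report release duration as appropriate; no specified output says so. What remains is the sentence itself, which gives an unsupported conclusion if followed.

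Second, the rule does not mention 45 hours. A reader might take the plan to say that a lower pH demonstrates 45-hour release, but the link is an inference. It is a reasonable one, since no other duration appears. If something else was meant, the word *appropriate* has no stated standard.

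Third, the reading is not empty. It might be thought to say nothing about duration, but that goes too far: a drop gives a lower bound near the elapsed time, subject to attribution, and an absent drop on schedule is evidence against 45 hours.

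Fourth, one might conclude that every Day 8 reading lies past 45 hours, or that only readings from 45 hours onward should inform duration. The first depends on the clock time of the Day 6 dose. The second would discard early readings that could contradict the 45-hour figure, and would rely on late ones where an absent drop is uninformative.

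**Conclusion.** The point holds as a matter of interpretation. A lower pH at the Day 7 visit shows at most an effect still present when it was measured; it does not establish the roughly 45 hours described elsewhere, and an absent drop at a late visit does not refute it. Nominally, the on-schedule reading falls 21 hours short of 45. If all 24 planned patients attended on Day 7, no reading would nominally lie beyond it.

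This rests on three assumptions: that 45 hours is the duration meant, that the Day 6 dose is taken on Day 6, and, for the nominal figures, that dose and visit fall at similar clock times. The calendar-day limits drop the third. The consequence is minor: it touches one exploratory, descriptive variable, and a reader should not extend it to the cure-rate analysis, which does not use pH.

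**What to change.** In Protocol 7.2 and SAP 7.10.1, replace the inference with wording such as: *a lower pH indicates that a pH effect is still present at the time of reading*. Make no claim of appropriate release duration from the pooled Day 7 change.

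Show the pH change from Day 0 by time since the last pessary. Use hours if insertion and reading times were recorded or can still be obtained; otherwise use actual visit day (7, 8, 9), which follows from visit dates and SAP relative day. The second route may be the only one left. The SAP was finalised on 2020-01-14, whereas the protocol planned the last patient out in February 2019, so on that timetable a new eCRF time field would have come too late.

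Both documents should also reconcile the plural reference to follow-up visits in the rule with the single post-baseline reading that is scheduled.

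The cost is one sentence in each document and one split in an existing descriptive table; dosing and visits are untouched. The drawbacks are that the subgroups will be small with 24 patients, and that the duration claim may have to be dropped.
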